9. ADVERSE EVENTS/SERIOUS ADVERSE EVENTS

9.1. ADVERSE EVENTS - DEFINITION

An adverse event (AE) is any undesirable event that occurs to a subject during a study, whether or not that event is considered study drug-related. Monitoring for AEs will start at dosing. Examples include:

- Any treatment-emergent signs and symptoms (events that are marked by a change from the subject's baseline/entry status [e.g., an increase in severity or frequency of pre-existing abnormality or disorder])
- All reactions from study drug, an overdose, abuse of drug, withdrawal phenomena, sensitivity or toxicity to study drug
- Apparently unrelated illnesses
- Injury or accidents (Note: if a medical condition is known to have caused the injury or accident, the medical condition and the accident should be reported as two separate medical events [e.g., for a fall secondary to dizziness, both "dizziness" and "fall" should be recorded separately])
- Extensions or exacerbations of symptoms, subjective subject-reported events,

new clinically significant abnormalities in clinical laboratory, physiological testing or physical examination

All AEs, whether or not related to the study drug, must be fully and completely documented on the AE page of the electronic Case Report Form (eCRF) and in the subject's clinical chart.

In the event that a subject is withdrawn from the study because of an AE, it must be recorded on the eCRF as such. The subject should be followed and treated by the Investigator until the abnormal parameter or symptom has resolved or stabilized.

The Investigator must report all directly observed AEs and all spontaneously reported AEs. The Investigator will ask the subject a non-specific question (e.g., "Have you noticed anything different since your dose of the study medication?") to assess whether any AEs have been experienced since the last assessment. AEs will be identified and documented on the eCRF in appropriate medical terminology. The severity and the relationship to the study drug will be determined and reported on the CRF (see below).

9.2. ADVERSE EVENTS - SEVERITY RATING

The severity of each AE should be characterized and then classified into one of three clearly defined categories as follows:

- Mild the AE does not interfere in a significant manner with the subject's normal functioning level. It may be an annoyance.
- Moderate the AE produces some impairment of functioning but is not hazardous to health. It is uncomfortable or an embarrassment.
- Severe the AE produces significant impairment of functioning or incapacitation and is a definite hazard to the subject's health.

These three categories are based on the Investigator's clinical judgment, which in turn depends on consideration of various factors such as the subject's report, and the physician's observations. The severity of the AE should be recorded in the appropriate section of the Adverse Event CRF.

9.3. Adverse Events - Relationship to Study Drug

The relationship of each AE to the study drug will be classified into one of three defined categories as follows:

- Unlikely a causal relationship between the AE and the study drug is unlikely.
- Possible a causal relationship between the AE and the study drug is possible.

Page 30 of 39

• Probable – a causal relationship between the AE and the study drug is probable. For example, the AE is a common adverse event known to occur with the pharmacological class the study drug belongs to; or the AE abated on study drug discontinuation and reappeared upon re-challenge with the study drug.

These three categories are based on the Investigator's clinical judgment and consideration of various factors such as the subject's report, the timing of the AE in relationship to study drug administration/discontinuation, the Investigator's observations and the Investigator's prior experience. The relationship of the AE to the study drug will be recorded in the eCRF.

9.4. SERIOUS ADVERSE EVENTS AND UNEXPECTED ADVERSE EVENTS - DEFINITIONS

A Serious Adverse Event (SAE) includes (but is not limited to) an experience occurring at any dose that results in any of the following outcomes:

- Death
- A life-threatening event (i.e., the subject is at immediate risk of death from the reaction as it occurs). "Life-threatening" does not include an event that, had it occurred in a more serious form, might have caused death. For example, drug-induced hepatitis that resolved without evidence of hepatic failure would not be considered life-threatening even though drug-induced hepatitis can be fatal.
- In-patient hospitalization (hospital admission, not an emergency room visit) or prolongation of existing hospitalization.
- A persistent or significant disability/incapacity (i.e., a substantial disruption of the subject's ability to carry out normal life functions).
- A congenital anomaly/birth defect.

In addition, medical and scientific judgment should be exercised in deciding whether other situations should be considered an SAE (i.e., important medical events that may not be immediately life-threatening or result in death but may jeopardize the subject or may require medical or surgical intervention to prevent one of the other outcomes listed in the definition above). Examples of such medical events include (but are not limited to): allergic bronchospasm requiring intensive treatment in an emergency room or at home, blood dyscrasias or convulsions that do not result in in-patient hospitalization, or the development of drug dependency or drug abuse.

An **unexpected** AE is one for which the specificity or severity is not consistent with the current Investigator's Brochure. For example, hepatic necrosis would be unexpected (by virtue of greater severity) if the Investigator's Brochure only listed elevated hepatic enzymes or hepatitis.

Similarly, cerebral thromboembolism and cerebral vasculitis would be unexpected (by virtue of greater specificity) if the Investigator's Brochure only listed cerebral vascular accidents.

9.5. SERIOUS ADVERSE EVENTS REPORTING

The reporting of SAEs by the Sponsor to Regulatory Authorities (e.g., FDA) is a regulatory requirement.

All SAEs must be reported immediately (within 24 h of learning of the event) by telephone or notification via email through the EDC system to:

[name], MD Cassava Sciences, Inc. Email: [contact] [contact]

Do not delay reporting a suspected SAE to obtain additional information. Any additional information, if collected, can be reported to the Sponsor as a follow-up to the initial report.

A completed SAE report form must be sent within five (5) working days to the medical monitor. The Sponsor will report SAEs to the IRB and FDA as required.

In the case of a death or other SAE that has occurred within 30 days after receiving study drug, the Principal Investigator must also report such an event within 24 hours of being notified.

In the event of any SAE (other than death), the subject will be instructed to contact the study physician (Principal Investigator or designee) using the phone number provided in the ICF. All patients experiencing an SAE will be seen by a Principal Investigator or designee as soon as feasible following the report of an SAE.

10. STATISTICAL CONSIDERATIONS

10.1. ANALYSIS POPULATIONS

All patients who receive study medication will be included in safety analyses. All patients who have sufficient data for biomarker, ADAS-Cog11, NPI and GDS analyses will be included in the analysis population for each measure individually.

10.2. Pharmacokinetic Parameters

The only plasma PK parameters to be collected from this study are the C_{min} values from blood samples taken prior to dosing at Months 15 and 18.

10.3. STATISTICAL ANALYSIS

Biomarker endpoints to be analyzed include: 1) CSF A β_{42} , 2) CSF total tau 3) CSF ptau181, 4) CSF neurofilament light chain, 5) CSF neurogranin, 6) CSF sTREM2, 7) plasma neurofilament light chain, 8) plasma neurogranin, 9) plasma total tau, 10) plasma A β_{42} , 11) SavaDx lymphocyte assay, 12) SavaDx plasma assay and 13) mTOR assay. These data will be analyzed by paired t test comparing baseline to Month 6 or Month 12. Other appropriate statistics may be performed to compare mild versus moderate patients.

The ADAS-Cog11, NPI and GDS endpoints will be analyzed by linear regression with pre-planned comparisons of mild versus moderate patients. Other appropriate statistics may be performed.

Month 12 to Month 18 ADAS-Cog11, NPI and GDS data will be analyzed by mixed model repeated measures (MMRM) analysis. Month 6/12 to Month 18 CSF biomarker data will be analyzed by ANCOVA for the effect of treatment with Month 6/12 value as the covariate, or by ANOVA.

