4. SUMMARY OF STUDY DESIGN

The first 12 months is an open-label treatment of simufilam 100 mg b.i.d. for patients who completed prior Phase 2 studies PTI-125-02 and PTI-125-03. New patients are included so that up to 200 patients are enrolled in this study. Month 12 to Month 18 is a randomized withdrawal phase; patients will be randomized to continue taking simufilam 100 mg b.i.d. or matching placebo. Month 18 to Month 24 will be an additional 6 months of open-label simufilam 100 mg b.i.d. Simufilam and placebo will be administered as coated oral tablets. Patients who were enrolled prior to this amendment can continue upon reconsenting to the randomized withdrawal and final 6-month open-label portion.

All patients will provide consent to enroll into this study. Unless patients have a prior positive amyloid PET scan, MRI showing hippocampal volume loss or other prior evidence of AD, patients will undergo a CSF draw (if all other screening criteria are met) to confirm a total tau/A β_{42} ratio ≥ 0.28 .

Patients will report to the clinic in the morning of Day 1. Prior to dosing, patients will complete the following baseline measures: ECG, vital signs, clinical labs, urinalysis, listen to heart and lungs, ADAS-Cog11, neuropsychiatric inventory (NPI), geriatric depression scale (GDS), and the C-SSRS. A blood sample will be collected for plasma-based biomarkers and genetic testing.

Patients will return to the clinic every month through Month 3 and every 1.5 months through Month 12. Visits on Months 4.5, 7.5 and 10.5 will include vital signs, listening to heart and lungs, AE monitoring, C-SSRS, and drug dispensation and accountability only and may be conducted by telemedicine, based on the judgement of the Investigator. After Month 12, visits will be on Months 13, 15, 18, 21 and 24. Patients completing Month 12 prior to availability of drug supply for the randomized withdrawal phase will continue with active treatment until drug supply is ready and therefore will have an additional "Withdrawal Day 1" visit before resuming with the Month 13 visit one month later.

PK blood samples will be obtained in the morning before dosing at return visits on Months 15 and 18.

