Blood draws for clinical laboratory testing and urine collection for urinalysis will be performed at Day 1 and Months 1, 2, 3, 6, 9, 12, 15, 18, 21 and 24. Safety assessments of vital signs and listening to heart and lungs will be conducted at all visits. ECGs will be conducted on Day 1 and Months 1, 3, 6, 9, 12, 18 and 24.

For plasma biomarkers, plasma samples will be collected on Day 1 prior to dosing and on Months 3, 6, 9, 12, 15, 18, 21 and 24. Plasma markers include SavaDx, the complementary diagnostic/biomarker, and a subset of CSF biomarkers (NfL, neurogranin, total tau, $A\beta_{42}$ and YKL40). For the first 50 patients who provided a screening CSF sample, an additional CSF sample will be collected at Month 6 or Month 12 (25 patients each Month 6 and Month 12). This sample will be used to assess CSF biomarker changes. These CSF draws will, however, become OPTIONAL after 50 patients have provided either a Month 6 or Month 12 CSF sample. Further, these optional Month 6 or Month 12 samples should NOT be obtained from patients who did not provide a CSF sample at screening.

An independent Data Safety Monitoring Board (DSMB), will meet periodically to review patient safety assessments and determine if dosing may continue.

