7.2.6. Follow-up Visits on Months 4.5, 7.5 and 10.5

Patients will return to clinic at any time of day. The visit may be conducted by telemedicine, based on the judgement of the Investigator.

The following assessments will be conducted:

- Vital signs (blood pressure, temperature, pulse and respiratory rate), and weight
- Listen to heart and lungs
- Adverse event monitoring
- C-SSRS Since Last Visit version. If the C-SSRS indicates imminent risk for suicidality, defined as the patient positively endorsing questions 4 or 5 of the suicidal ideation section or any suicidal behavior questions, discontinue study drug and refer for appropriate care.

7.2.7. Follow-up Visits on Month 6 and 18

Patients will return to the clinic in the morning on the Month 6 Visit. Those patients undergoing a CSF draw will take their morning dose upon arrival (time of dosing to be recorded).

Patients will return to clinic in the morning before taking their morning dose.

Within 30 min prior to dosing, the following assessments will be conducted:

- Blood sample collection for PK assessment (for Cmin Month 18 only)
- Clinical laboratory tests (blood and urine)
- Plasma sample collection (from 8 mL whole blood) for SavaDx and other plasma biomarkers.

After dose, the following assessments will be conducted:

- Vital signs (blood pressure, temperature, pulse and respiratory rate), and weight
- Listen to heart and lungs

- Adverse event monitoring
- ECG
- ADAS-Cog11, NPI, GDS, and C-SSRS Since Last Visit version. If the C-SSRS indicates imminent risk for suicidality, defined as the patient positively endorsing questions 4 or 5 of the suicidal ideation section or any suicidal behavior questions, discontinue study drug and refer for appropriate care.
- CSF sample collection at Month 6 (time post-dose to be recorded) only for the first 25 patients with a baseline CSF. (The next 25 patients with a baseline CSF will have CSF drawn at Month 12). Month 18 CSF draw is OPTIONAL for patients who provided a Month 6 or Month 12 CSF and is not an option for any other patients.

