1.3 Study Objectives

The overall study objective is to assess the long-term safety and tolerability of simufilam.

This study has separate sets of objectives for the OL and RW phases. Safety and tolerability are the primary objectives of the OL phase. The primary objective of the RW phase is to assess patient response to blinded, randomized drug withdrawal.

Because drug safety in non-responders can be a critical component of a drug's risk-reward assessment, all patients who completed the 12-month OL phase were eligible to enter the RW phase, regardless of whether they previously showed an apparent response (or not) to open-label drug treatment.

Some study objectives overlap in the OL and RW phases. Hence, objectives are summarized separately below for the OL and RW phases, and for objectives spanning multiple phases. All objectives apply to mild-to-moderate Alzheimer's Disease (AD) patients, 50-85 years of age.

Objectives for the Open-label (OL) phase

- Assess the long-term safety and tolerability of OL treatment with simufilam 100 mg b.i.d. during 12-month repeat-dose oral administration.
- Assess mean changes from baseline on MMSE and compare those changes between patients with mild vs moderate AD.

Objectives for the Randomized Withdrawal (RW) phase

- Assess the safety and tolerability of treatment with simufilam 100 mg b.i.d. versus matching placebo over the 6-months study period.
- Assess patient response to blinded, randomized drug withdrawal on ADAS-Cog11.

Objectives Spanning Overall Study

Exploratory objectives tested across multiple phases are to:

- Characterize the safety and tolerability of simufilam during and up to 24 months of treatment.
- Assess mean changes from baseline on biomarkers and compare those changes between patients with mild vs moderate. For CSF biomarkers, change from baseline to M6 or M12 will be calculated. Plasma biomarkers will be analyzed for change from baseline to M6 and M12 for the OL phase and from M12 to M18 for the RW phase.

Note: All biomarker assessments in this study are exploratory endpoints that are not patient safety related, are 'Research Use Only' products, and, hence, are not intended to be compliant with FDA's Quality System Regulation (QSR) or ISO equivalent.

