5.1 Efficacy Analysis

General Considerations

Efficacy and biomarker analyses will be based on the FAS analysis set. No adjustments for multiple comparisons will be made. Baseline values for each endpoint are defined as the last non-missing value taken on or prior to Day 1.

Unless otherwise specified, for continuous endpoints that are scheduled to be assessed at only 1 post-baseline visit (MMSE-2), mean changes from baseline will be analyzed using ANCOVA. The analysis will include the categorical, fixed effect of enrollment group (mild vs. moderate AD) along with the continuous, fixed covariate of baseline value of the endpoint being analyzed (baseline). Significance tests comparing endpoint LSMEANS by enrollment group (mild vs. moderate) will be based on least-squares means. Significance of within-group mean changes from baseline will also be reported.

Biomarker exploratory endpoints

Biomarker endpoints to be analyzed may include: 1) CSF Aβ42, 2) CSF tau 3) CSF p- tau181, 4)Version 3.0CONFIDENTIAL, MATERIAL NON-PUBLIC INFORMATIONPage 15 of 19

CSF neurofilament light chain, 5) CSF neurogranin, 6) CSF sTREM2, 7) CSF YKL40 8) CSF HMGB1 9) plasma neurofilament light chain, 10) plasma GFAP, or other non-safety related exploratory biomarkers of disease.

Plasma biomarker data may be analyzed with the MMRM model described above. CSF biomarker data may be analyzed by descriptive statistics.

Note: All biomarker assessments in this study are exploratory endpoints that are not patient safety related; are 'Research Use Only' products; and, hence, are not intended to be compliant with FDA's Quality System Regulation (QSR) or ISO equivalent.

Clinical endpoints

The ADAS-Cog11 will be analyzed using the MMRM model described above. MMSE will be analyzed by ANCOVA.

6 Analysis of Randomized Withdrawal Phase

The following efficacy analyses will be applied to data from the RW phase, which begins after the month 12 assessment and continues through month 18.

These analyses are similar to the analyses from the Open-Label phase except:

- 1) treatment group replaces enrollment group in the analysis models
- 2) baseline value is defined as the last non-missing value at or prior to month 12; or, for patients who were maintained on open-label treatment beyond month 12, baseline is defined as the last non-missing value at or prior to the withdrawal day 1 assessment.

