Significance tests comparing mean changes from baseline by treatment group will be based on least-squares means. Significance of within-group mean changes from baseline will also be evaluated.

Biomarker Endpoints

Biomarker endpoints to be analyzed may include: 1) CSF A β 42, 2) CSF tau 3) CSF p- tau181, 4) CSF neurofilament light chain, 5) CSF neurogranin, 6) CSF sTREM2, 7) CSF YKL40 8) CSF 1) plasma neurofilament light chain, 2) plasma GFAP.

Plasma biomarker data may be analyzed with the MMRM model described above.

Clinical Endpoints

The ADAS-Cog11 will be analyzed using the MMRM model described above.

7 Analysis of Follow up to Randomized Withdrawal Phase (Openlabel)

The follow up phase is defined as beginning after the month 18 Visit through the month 24 assessment. The following efficacy analyses will be applied to the follow up data.

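### The randomized-withdrawal CSF change pools 12-month changes that start at Month 6, half of that time before randomization, with 6-month changes that start at Month 12

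*Protocol*

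**What the plan says.** **Randomized period.** Protocol section 4: "Month 12 to Month 18 is a randomized withdrawal phase".

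**Who has which CSF sample.** Protocol section 4 plans one on-treatment CSF sample for each of 50 patients who gave a screening sample, 25 at Month 6 and 25 at Month 12. Protocol 7.2.7 takes the Month 6 sample "only for the first 25 patients with a baseline CSF"; the next 25 are drawn at Month 12. Under 7.2.8 a Month 12 draw is optional for anyone already sampled at Month 6. Under 7.2.7 a Month 18 draw is optional for both groups.

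**Protocol analysis.** Section 10.3: "Month 6/12 to Month 18 CSF biomarker data will be analyzed by ANCOVA for the effect of treatment", then "with Month 6/12 value as the covariate, or by ANOVA". Sampling month does not appear in the model, and no separate analysis by sampling month is given. In the same section the cognitive and neuropsychiatric scales are analyzed from Month 12 to Month 18.

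**SAP.**
- Section 6 sets the withdrawal-phase baseline: "baseline value is defined as the last non-missing value at or prior to month 12". A later clause covers patients kept on open-label drug beyond Month 12.
- Section 1.3: "For CSF biomarkers, change from baseline to M6 or M12 will be calculated". The same objective gives plasma markers a Month 12 to Month 18 change for the withdrawal phase and gives CSF none.
- Section 5.1 says CSF may be summarized descriptively. Section 6.1 lists CSF markers among those that may be analyzed in the withdrawal phase, but names a model only for plasma.
- Section 6.1 also says: "Significance of within-group mean changes from baseline will also be evaluated".

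**The concern.** Take two patients who both give a Month 18 sample. One was last sampled at Month 6, the other at Month 12. Both feed the same withdrawal-phase CSF endpoint, but the intervals differ in length and in what they contain. The Month 6 patient's change includes six months on open-label simufilam, whichever arm that patient later joins. In the placebo arm, time on drug is then counted as change on withdrawal.

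At stake is the meaning of any mean CSF change by arm shown under a withdrawal-phase heading. A secondary issue is avoidable noise in the arm comparison: nothing in the plan balances the Month 6/Month 12 mix between arms, and one covariate slope has to serve two different lags.

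**Working it through.** The documents give no SD, effect size, power or sample size for the CSF comparison, so there is no figure of the plan's own to reproduce.

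**1. Interval per patient (on schedule).** Inputs: randomization at Month 12, final sample at Month 18.
- Month 6 start: 18 - 6 = 12 months, of which 12 - 6 = 6 (50%) precede randomization.
- Month 12 start: 18 - 12 = 6 months, of which 0 precede randomization.

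The SAP rule does not change this. With no Month 12 CSF, the last available value is the Month 6 one.

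**2. Pooled time.** Assume the 25/25 split carries through to Month 18 and no Month 6 patient takes the optional Month 12 draw.
- Mean interval = (25 x 12 + 25 x 6)/50 = 450/50 = 9 months, against 6.
- Share before randomization = (25 x 6)/450 = 150/450 = 33%.
- For mixes from 5:20 to 20:5 (Month 6:Month 12), the share is 30/180 = 17% to 120/270 = 44%.

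**3. Within-arm change.** Let s be the slope per month in the withdrawal phase, r the open-label slope divided by s, and p the fraction of Month 6 starters in the arm.
- Pooled mean change = p(6rs + 6s) + (1 - p)6s = 6s(1 + pr).
- True withdrawal-phase change = 6s, so the ratio is 1 + pr. At p = 0.5 it is 1 + 0.5r.

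| r | Meaning | Ratio at p = 0.5 | Error |
|---|---|---|---|
| 0 | marker flat from Month 6 to Month 12 | 1.0 | none |
| 1 | same slope before and after randomization | 1.5 | +50% |
| -1 | equal and opposite slopes | 0.5 | -50% |

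The documents do not fix r, so neither the size nor the direction of the error is known.

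**4. Between-arm contrast.** Both possible start samples precede randomization, so neither the start value nor its timing can depend on the arm, and the expected contrast is the treatment effect. A simulation agrees: 4,000 runs, 50 patients, assumed true effect 0.30 SD, drift 0.05 SD per month, 6-month correlation 0.9. The pooled ANCOVA estimate averaged 0.294, or 0.296 with sampling month and its interaction with the start value added. In the same runs the control-arm mean change was 0.61 SD from a Month 6 start and 0.30 SD from a Month 12 start.

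**5. Precision.** Assumptions: 40 patients, between-patient SD 1, 6-month within-patient SD 0.3, assay SD 0.1. The variance of the arm contrast without a sampling-month term, divided by the variance with it, was:
- 0.99 at drift 0.1 SD per 6 months: no gain;
- 1.04 at 0.2: a cut of 1 - 1/1.04, about 4%;
- 1.10 at 0.3: a cut of 1 - 1/1.10, about 9%.

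Dropping the Month 6 starters would be worse. For assumed 6-month correlations of 0.95 to 0.70, and Month 18 CSF from all 50, the difference detectable with 80% power is 0.30 to 0.63 SD pooled (25 per arm) and 0.35 to 0.80 SD with only the 25 Month 12 starters (about 12.5 per arm).

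**6. Drug-supply delay.** Patients held on open-label drug after Month 12 have no CSF draw at the Withdrawal Day 1 visit (Protocol 7.2.9 and Appendix A). For an assumed delay of d months, the open-label share is d/(6 + d) from a Month 12 start and (6 + d)/(12 + d) from a Month 6 start. At d = 1 to 3 that is 14% to 33% and 54% to 60%. The documents do not give the length of the delay.

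**The case against.** The strongest reply is that the current SAP may not run this analysis at all. The ANCOVA is in Protocol 10.3 only. The SAP's CSF objective stops at Month 6 or Month 12, its CSF method is optional and descriptive, and its withdrawal-phase model is named for plasma. This stands as a limit: SAP version 3.0 does not clearly retain the protocol's test. It does not say that the test was dropped either, although section 1.1 undertakes to explain material departures from the protocol's methods. A descriptive withdrawal-phase summary would mix the two intervals in the same way.

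Other parts of the reply also stand:
- A reader might infer that the treatment comparison is biased. It is not, because both start samples precede randomization.
- A reader might infer that the SAP commits to within-arm significance tests on CSF. The sentence in 6.1 follows the repeated-measures paragraph for endpoints with more than one post-baseline visit, and CSF has one in this phase. Section 6 does carry over the open-label approach, which reports within-group significance for single-visit endpoints, but only where nothing else is specified. The commitment is uncertain.
- A baseline precedes its phase by definition, and the protocol states the two start months openly. There is no contradiction in the text; the gap is that the two are not separated.
- Where both samples exist, the SAP rule already selects Month 12. Protocol 10.3 does not say which is used.
- The open-label wording on Month 6 or Month 12 can be read as two separate comparisons. The request there is only to say so.

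**Conclusion.** The point holds as a cheap improvement to an exploratory endpoint. As written, the withdrawal-phase CSF change pools 12-month and 6-month changes. For an on-schedule patient sampled only at Month 6, half of the interval precedes randomization. Within-arm or descriptive CSF results for this phase are therefore not changes over withdrawal.

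The 33% pre-randomization share assumes full Month 18 uptake and no optional Month 12 repeats; the actual number with Month 18 CSF is not given. A flat statement that the withdrawal change is overstated by 50% is tempting but unsupported: it needs equal slopes before and after randomization, and the error runs from -50% to +50% as r goes from -1 to 1. The arm contrast is unbiased in expectation. A sampling-month term reduces its variance by about 0% to 9%, under drift and SD values that are assumed.

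**What to change.** - **Protocol 10.3 and SAP 6.1:** report within-arm withdrawal-phase CSF change in separate rows for Month 12-start and Month 6-start patients. Label the Month 6-start rows as 12-month changes that include 6 open-label months.
- **Pooled arm contrast, if kept:** keep all patients and add sampling month (6 or 12) as a factor in the ANCOVA.
- **Protocol 10.3:** state that Month 12 is the start value where both samples exist, as the SAP rule already implies.
- **SAP 6.1:** state whether the protocol's CSF ANCOVA is kept or replaced by descriptive summaries.
- **SAP 1.3 and 5.1:** report open-label CSF change separately at Month 6 and at Month 12.
- **Delayed patients:** show the actual interval, since their Month 12 start also includes open-label time.

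No new data are needed. The cost is smaller groups per row and one degree of freedom in the pooled model. SAP 1.2 says versions 1.0 and 2.0 were already used for the open-label and withdrawal-phase analyses, so a factor added now should be marked in the study report as added after them.
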